## 6.8 Outcome Measures

**Primary effectiveness outcome:** HF GDMT prescription increased (new class added, dose titrated upward on existing medication, or switch to ARNI from ACEi/ARB), within 30 days of index visit.

**Secondary effectiveness outcomes:**

- HF GDMT prescription increased (new class added, dose titrated upward on existing medication, or switch to ARNI from ACEi/ARB), within 60 and 90 days of index visit.
- Addition of SGLT2i or ARNI (including switch from ACEi/ARB to ARNI), within 30, 60, and 90 days of index visit. This will be analyzed primarily using the entire eligible

sample and secondarily only among those who have not already been prescribed SGLT2i or ARNI prior to the intervention.

**Other pre-specified effectiveness outcomes:**

- All-cause mortality or emergency visit or hospitalization for heart failure, within 365 days of index visit. This will be assessed as patient death (yes/no), patient with emergency visit with a primary diagnosis of heart failure (yes/no), or admission for inpatient hospitalization with primary diagnosis of heart failure (yes/no).
- Optimal GDMT dosing (at least 50% of target dose) on all classes (with or without ARNI), within 180 days of index visit.
- Increased dosing or initiation for each individual class, within 180 days of index visit.
- Decreased dosing or removal for each individual class, within 180 days of index visit.
- Timing of increases in GDMT over 180 days since index visit.
- Economic outcomes such as (1) return on investment (ROI) and (2) cost effectiveness (CE) of CDS and MTDM interventions compared with standard of care (using modeling approaches specified in the ROI and CE analysis section above).

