### 3. ABSTRACT

#### GREAT- HF Care

- Background and Rationale - Heart failure with reduced Ejection Fraction (HFrEF) is associated with high mortality and adverse events (hospitalization or urgent outpatient visits for heart failure (HF)), along with diminished quality of life. Despite convincing data that evidenced-based, guideline-directed medical therapies (GDMT) improve mortality and heart failure-related events, there remains insufficient utilization of these life-saving drugs (evidence-based beta-blockers (EBBB), angiotensin-neprilysin inhibitors (ARNI)/ angiotensin converting enzyme inhibitors (ACEi)/ angiotensin receptor blockers (ARB), mineralocorticoid receptor antagonists (MRA) and sodium-glucose cotransporter 2 inhibitors (SGLT2i)) in patients with HFrEF.
- Objectives - The primary objective of this study is to implement and evaluate a multifaceted, interdisciplinary intervention to improve GDMT use, reduce mortality, and reduce future heart failure events in patients with HFrEF.
- Study Design – We will conduct a cluster-randomized controlled trial at the level of the clinician comparing two multi-faceted interventions to usual care with or without systemic education within a population of patients with HFrEF seen at a Geisinger cardiology clinic who are not on complete GDMT.
- Population - Patients at least 18 years of age with documented HFrEF or Left Ventricular Ejection Fraction (LVEF) < 40 (within two years prior to the triggering visit) who have an outpatient encounter with the Geisinger Cardiology department (office visit or telemedicine). Patients must also not currently be on optimal GDMT according to their electronic health records (EHR), as reflected in use of medications in fewer than four of the recommended classes or in all four classes but not ARNI. And patients must not currently be in hospice or palliative care or allergic to all non-prescribed GDMT. The clinician target population comprises clinicians practicing at one or more Geisinger outpatient cardiology clinics who manage care for patients with HFrEF and include cardiologists (MD/DO), nurse practitioners, and physician assistants.

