## **6.6 Exclusion Criteria**

Currently in hospice or palliative care. (ICD 10 code: Z51.5)

Patient has been prescribed medications from all four categories of GDMT, including ARNI specifically.

Patient has a documented allergic reaction to each class of GDMT not presently prescribed.

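### The 180-day optimal-dosing outcome can already be met at entry, and the CDS models have no patient-level term for index status

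*Combined protocol and SAP*

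**What the plan says.** **Eligibility.** The abstract defines sub-optimal therapy as "use of medications in fewer than four of the recommended classes or in all four classes but not ARNI". Section 6.6 excludes a patient only under the matching condition, "Patient has been prescribed medications from all four categories of GDMT, including ARNI specifically", or for hospice or palliative care, or for allergy to every class not prescribed. None of these refers to dose.

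**Optimal dosing.** Section 6.8 counts "Optimal GDMT dosing (at least 50% of target dose) on all classes (with or without ARNI), within 180 days of index visit". It gives no change-from-index condition, no restriction to patients below that level at index, and no scoring rule for those already there. I read it as requiring all four classes. The primary outcome, the secondary outcomes and the per-class outcomes are all worded as changes.

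**SGLT2i/ARNI.** The secondary outcome is "Addition of SGLT2i or ARNI (including switch from ACEi/ARB to ARNI), within 30, 60, and 90 days of index visit". It is analysed first in the whole eligible sample and then restricted: "sample and secondarily only among those who have not already been prescribed SGLT2i or ARNI prior to the intervention".

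**Models.** Section 7.2.3 specifies OLS with clinician-clustered robust standard errors. In section 7.2.2 the CDS models carry education arm and its interaction with CDS. Baseline prescribing rates enter the CDS models only in exploratory versions, as clinician characteristics. The education models do adjust for baseline prescribing rates, but these are not described as the patient's own index status.

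**The concern.** A patient on a beta-blocker, an ACEi or ARB, an MRA and an SGLT2i is eligible because ARNI is missing. If each drug is at half of target or more, that patient meets the 180-day outcome on day 0, and still meets it if nobody changes a prescription. The patient adds the same success to every arm and says nothing about the intervention.

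This has two consequences. The whole-sample difference is smaller than the difference among patients who could still change, with extra variance on top. Also, any chance difference between arms in the share already optimised passes straight into the unadjusted estimate. That matters most for CDS-MTDM, which has about 10 of the 103 current clinicians. Section 6.2 itself stratifies because of worries about unequal GDMT prescribing, so already-optimised patients may well cluster by clinician.

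A smaller, related point concerns the SGLT2i/ARNI outcome. Patients on both drugs who lack an MRA or beta-blocker are eligible and cannot score. The restricted analysis removes them, but its wording does not settle whether patients on exactly one of the two drugs stay in.

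**Working it through.** The plan gives no rate, effect or power for this outcome; section 7.1 covers GDMT prescribing within 30 days and the education contrast. So there is no figure to reproduce, only a range to bound.

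**1. How many could meet the outcome at index?** Inputs from section 4 (2018-2021): beta-blocker about 80%, ACEi/ARB/ARNI about 50% (ARNI 3.2-9.7%), MRA 16-22%, SGLT2i 1.3-4.6%.
- Upper bound for four classes without ARNI is the smallest class share. High end: min(4.6, 22, 80, 50 − 9.7 = 40.3) = **4.6%**. Low end: 1.3%.
- Under independence, high end: 0.046 × 0.22 × 0.80 × 0.403 = **0.33%**. Low end: 0.013 × 0.16 × 0.80 × 0.468 = 0.08%.

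Both come before the dose condition, which can only lower them. They describe all HFrEF patients in earlier years, not the eligible sample in the trial period.

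**2. Share of control successes present at entry** = b / [b + new × (1 − b)], where b is the share optimal at index and new is the control rate of new attainment by 180 days (not in the documents; assumed 4% to 15%).

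| b | new = 4% | new = 10% | new = 15% |
|---|---|---|---|
| 0.3% | 7% | 3% | 2% |
| 1% (assumed) | 20% | 9% | 6% |
| 3% (assumed) | 44% | 24% | 17% |
| 4.6% (cap) | 55% | 33% | 24% |

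**3. Dilution and power.** Whole-sample difference = (1 − b) × difference among those not optimal at index. At the cap, 5 points becomes 0.954 × 5 = 4.77 points.

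Illustration for CDS-OS v control: 1,935 patients per arm (45% of 4,300, assuming patients split as clinicians do), assumed 10% v 15% among those not optimal at index, assumed design effect 2. (The section 7.1 claim of 80% power for 5 points implies a design effect of about 1.2 to 2.8 over control rates of 10-50%, so 2 is not extreme.)
- b = 0.3%: power 0.91 with all patients unadjusted, 0.91 in those not optimal at index.
- b = 4.6%: 0.81 v 0.90.

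Adjusting the full sample for index status recovers nearly all of this if those already optimal stay so. The effect becomes (1 − b)δ and the residual variance about (1 − b)v, so the ratio of effect to standard error is scaled by √(1 − b), as in the restricted analysis.

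**4. Chance imbalance, CDS-MTDM v control.** SE of the index difference = √[p(1 − p)(1/430 + 1/1,935) + sd²(1/10 + 1/46)], with sd the between-clinician SD (assumed) and 10 v 46 taken from 103 current clinicians.
- p = 0.3%, sd = 0.3 points: 0.31 points.
- p = 3%, sd = 3 points: 1.39 points.
- p = 4.6%, sd = 4 points: 1.79 points.

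If all 52 reserved places for new clinicians were filled (15.5 v 69.75 clinicians), the last two become 1.24 and 1.58.

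**5. SGLT2i/ARNI.** At the highest section 4 rates and independence:
- On both: 0.046 × 0.097 = 0.4% (ceiling 4.6%).
- On exactly one: 0.046 × 0.903 + 0.097 × 0.954 = 13.4%.

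The restricted set therefore differs by about 13% of patients according to whether the wording means on neither drug or not on both. If each drug were used by 30% (pure assumption), the figures would be 9% and 42%.

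**The case against.** **The arms are randomised.** This is the strongest reply, and it stands. Index status is equal in expectation across CDS arms, randomisation was stratified because of prescribing differences, and variation from index status is part of what clinician-clustered standard errors measure. A reader might infer that the CDS estimates are systematically biased; the documents do not support that. What remains is precision and protection against chance imbalance in an arm of about 10 clinicians.

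**The affected group may be tiny.** Also fair. A reader might infer that most control successes were present at entry. Shares above one half need both the 4.6% cap and low new attainment; under independence the share is 2-7%. An entry share such as 10% exceeds anything the section 4 figures allow. Use may have risen since 2021, but the documents give no later figure.

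**The ARNI phrase may denote two versions of the outcome.** If so, the version requiring ARNI cannot be met at index, because section 6.6 excludes those patients. The point then applies only to the other version.

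**SGLT2i/ARNI is already handled by index status.** Largely correct. A reader might infer that this outcome, too, ignores index status. It does not: it is scored as an addition or switch, and a restricted analysis is planned. Either reading of the restriction removes patients on both drugs, and patients on exactly one remain in the lead analysis. Only the ambiguous definition and the unadjusted full-sample model are left.

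**Baseline rates are in the education models.** True, but they are not stated to be patient-level, and the CDS models have them only as exploratory clinician covariates.

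**Conclusion.** The gap is real and modest. The optimal-dosing outcome, in the version not requiring ARNI, can be met at entry by patients whom the criteria admit, and neither its definition nor the CDS models take account of this. The consequence in the randomised comparisons is dilution, lost precision and exposure to chance imbalance, chiefly for CDS-MTDM.

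The size cannot be fixed from the documents. On 2018-2021 use it lies between almost nothing (about 0.3% of patients, power unchanged) and a noticeable loss (4.6%, with 5 points diluted to 4.77 and power 0.81 rather than 0.90 in the illustration). The dose condition pulls it down; any later rise in use pushes it up. The new-attainment rates, between-clinician SDs, design effect and patient split are my assumptions.

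The outcome is an other pre-specified one, and the primary outcome is already defined as a change, so the trial's main conclusion is untouched. The SGLT2i/ARNI point is a matter of clarifying a definition.

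**What to change.** **Optimal dosing (sections 6.8 and 7.2).** State whether the ARNI phrase means one outcome or two. Keep all patients in the analysis and add as a covariate whether the patient met the same definition at index. Report, as a supplement, the analysis among patients who did not meet it at index, and give the number already meeting it by arm.

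**SGLT2i/ARNI (section 6.8).** Define the restricted set as patients lacking at least one of the two drugs at index, and add index SGLT2i and index ARNI status as covariates in the full-sample model.

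**Cost.** A few sentences. Scoring upward titration already requires index medications and doses, so no new data are needed, and the full-sample intention-to-treat analysis is kept. Section 10 says that outcomes have not been extracted or examined by arm, apart from a limited check of alert function, so the change can still be made credibly before the data are seen.

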**Implementation Outcomes**

- We used the RE-AIM framework to evaluate Reach, Adoption, Implementation and Maintenance for each interventional strategy (effectiveness is measured as noted above). A summary of metrics is in Table 3.

**Table 3 Implementation Outcomes**

Variable	Reach	Adoption	Implementation	Maintenance
Focused Education	% of providers completing education	% of clinics receiving education	

• Feedback received from continuing education forms

• Adaptations made from original education plan

	Change in GDMT over time post education vs. control
CDS-OS	

• % of eligible patients where BPA action taken by provider

• % of eligible patients where the BPA SmartSet was opened

	% of eligible clinicians participating in the CDS intervention	Acknowledgement response assessment	Changes in %BPA action taken by providers over time.
CDS-MTDM	

• % of eligible patients where clinician referred to MTDM

• % of eligible patients seen by MTDM

	% of eligible pharmacists participating in the MTDM intervention	Fidelity to HFrEF protocol (e.g. % scheduled within 3 days)	Return on Investment of CDS-MTDM

## 7. STATISTICAL ANALYSIS PLAN

### 7.1 Power analysis

Data will be collected from 4,300 patients assigned to the clinicians in the study. With CDS-OS and CDS-MTDM (versus control), we expect to have 80% power to detect approximately 5 and 9 percentage-point increases, respectively, in prescribing GDMT within 30 days, at two-tailed  $p < .05$  with robust standard errors clustered at the clinician level. With education versus delayed education, we expect to have 80% power to detect an approximately 5.5 percentage-point increase in prescribing GDMT, with robust standard errors clustered at the clinician level. Power analyses were conducted using DeclareDesign.

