## 6. STUDY METHODS

### 6.1 Study Design

This is a cluster randomized study designed to evaluate the effectiveness of interventions aimed at improving GDMT in patients with HFrEF. Clinicians were stratified based on practice specialty, location, and pharmacist referral habits (see details below) and were permuted block randomized to achieve 45%/45%/10% proportional distribution across the following arms respectively: (1) usual care (**Control arm**); (2) multi-pronged CDS inclusive of a patient portal message about GDMT, an interruptive advisory upon chart entry advising clinicians of the need to optimize treatment, and a BPA that links to a GDMT order set

(**CDS-OS arm**); and (3) multi-pronged CDS as in #2 but replacing GDMT order set with referral to integrated clinical pharmacist co-management (**CDS-MTDM arm**). Secondarily, each of the 5 clinical practice sites of roughly equal HFrEF patient loads were assigned to receive either an early or delayed education rollout.

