The target audience for this education program are Cardiology clinicians (physicians (MD, DO) and advanced practitioners (PA, CRNP)) at Geisinger. Three clinics were selected for early education (i.e. before additional CDS and pharmacist referral interventions) and two clinics were reserved for late education (timed to occur after sufficient time has elapsed to assess the impact of the early education on its own). The early education programs were delivered over one month to each clinic with in-person attendance being encouraged.

Topics delivered in the early education sessions included:

1. Sacubitril / Valsartan (ARNI) in CHF
2. SGLT2 inhibitors in CHF
  - a. SGLT2i in Cardiovascular Disease & HFrEF
  - b. SGLT2i in HFrEF with Diabetes: What the Cardiologist should know
3. Management of HFrEF and chronic kidney disease (CKD)
4. Geisinger Pharmacist role in HFrEF

The early education sessions were delivered live, at each clinic location separately on a given date (either in-person or virtually depending on clinic preference).

Participants were encouraged by the lead PI to attend the live sessions if they were being offered at their clinic location. Continuing medical education (CME) credits were provided to attendees where applicable and lunch was provided during the live sessions. Presentations lasted about 30 minutes with a question-and-answer session to follow. An RSVP request was asked of those attending. Those missing their sessions were invited to a virtual session being held to try to increase attendance rates. The virtual sessions were recorded. The same approach will be used for delayed education.

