#### 7.2.2 Approach for comparisons across intervention arms

*CDS analyses:* We will test whether each outcome differs as a function of each CDS active arm (CDS-OS and CDS-MTDM) relative to no-CDS control. Regressions will include as covariates education arm and interactions between CDS and education. We will retain both terms if the interaction is significant and retain the main effect if only it is significant. The education variable in CDS analyses will be coded as delayed education (baseline), early education, other (for clinicians who were not in the system early enough to be included in an education arm, to avoid either diluting or biasing the education effects).

As an exploratory analysis, we will compare CDS-MTDM against CDS-OS to see which is most effective.

Additionally, covariates will be added to exploratory versions of the final models as sensitivity analyses, to adjust for measured differences across clinicians, such as role, number of patients seen, and baseline rates of prescribing each of the GDMT classes. We have no *a priori* hypotheses about the moderating effects of these covariates.

*Education analyses:* We will test whether each outcome differs as a function of early education relative to delayed education. Regressions will include as covariates CDS arm and interactions between CDS and education. We will retain both terms if the interaction is significant and retain the main effect if only it is significant. Assignment to early versus delayed education is not random; therefore, regression analysis comparing education to no-education controls will adjust for as many relevant covariates as possible, including baseline prescribing rates.

In these analyses, we will exclude clinicians who were not present throughout the data collection period, beginning at assignment to early education. That is, we only intend to include clinicians in early and delayed education arms who theoretically could have been exposed to the education and who then had time to treat patients based on what they learned.

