### 7.2.3 Regression Specifications

For all outcomes except timing of GDMT increases and ROI outcomes, ordinary least squares (OLS) regressions will be run with heteroskedasticity-robust standard errors clustered at the clinician level (to account for clustering of patients within clinicians). We will also explore the effect of clustering standard errors at the clinic level.

We will run a survival analysis to assess timing of GDMT increases.

Cost and outcomes estimate for the cost-effectiveness model will be obtained using EHR data, claims data, and literature-based sources. These data will be used to develop a decision tree analytical model with a state transition Markov cohort simulation to compute incremental cost effectiveness ratios (ICER), cost-effectiveness acceptance curves will be generated for all cost-effectiveness measurements. The effects of uncertainties from the model parameters will be evaluated by deterministic and stochastic sensitivity analyses. Following the World Health Organization's guidelines, we will define the willingness-to-pay (WTP) threshold as 1 to 3 times the local gross domestic product per capita. Interventions with an ICER below the threshold will be considered cost-effective. We will also compare the total dollar amount spent on implementing this program against the cost savings, if any, attributable to the interventions (CDS-OS + CDS-MTDM) to calculate the corresponding ROI.

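### Education was assigned non-randomly to five sites, but its main standard errors and its 80% power claim sit at clinician level, below the unit of assignment

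*Combined protocol and SAP*

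**What the plan says.** - **Assignment.** Section 6.1 states that "each of the 5 clinical practice sites of roughly equal HFrEF patient loads were assigned to receive either an early or delayed education rollout". Under Focused Education in Section 6.7, "Three clinics were selected for early education" and "two clinics were reserved for late education".
- **Mechanism.** Section 7.2.2: "Assignment to early versus delayed education is not random". The Interventions bullet of the Abstract (Section 3) says the opposite: it describes the early or late timing as randomized.
- **Adjustment.** Because of the non-random assignment, the education regression "will adjust for as many relevant covariates as possible, including baseline prescribing rates" (Section 7.2.2).
- **Standard errors.** Section 7.2.3 specifies OLS for all outcomes except timing and ROI, with "heteroskedasticity-robust standard errors clustered at the clinician level (to account for clustering of patients within clinicians". Clustering at clinic level is only to be explored.
- **Power.** Section 7.1 gives the education comparison "80% power to detect an approximately 5.5 percentage-point increase in prescribing GDMT, with robust standard errors clustered at the clinician level". It states no education sample size, control rate, ICC or site component.
- **Decision rule.** Section 7.2 applies two-tailed p<0.05 to all analyses. Section 10 names a primary education analysis, limited to encounters before delayed education began.

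**The concern.** Clinician clustering matches the CDS arms, which were randomized by clinician. It does not match education, where all clinicians at a site share one assignment. A clinician-clustered standard error treats clinicians at the same site as independent. Whatever the site has in common (case mix, local leadership, pharmacy access) then enters the education estimate without entering its standard error. With three sites against two, such differences do not average out.

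The plan gives reason to expect some site differences before adjustment: Section 6.2 stratifies the CDS randomization partly because of concern about prescribing imbalance across clinics. For HF specialists, though, it expects no significant difference by location.

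At stake is a contrast of three sites with two being reported as a significant education effect, supported by an 80% power figure and described as randomized by anyone who relies on the Abstract.

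**Working it through.** **Inputs from the documents.** Five sites, 3 early and 2 delayed (6.1, 6.7); 80% power for about 5.5 points with clinician clustering (7.1); two-sided 0.05 (7.2); 4,300 patients (7.1); 103 current clinicians (6.2). **Not in the documents:** control rate, clinician ICC, residual site SD, and the N of the education analysis. Values used for these are assumptions.

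**1. Is 5.5 points plausible at clinician level?** It cannot be reproduced strictly, but it can be checked for consistency. Assume N = 4,300 split 60/40 (2,580 and 1,720) and a control rate of 30%.
- Patients per clinician: 4,300/103 = 41.7.
- With clinician ICC 0.0203, the design effect is 1 + 40.7 × 0.0203 = 1.83.
- SE = √[1.83 × (0.355 × 0.645/2,580 + 0.30 × 0.70/1,720)] = 1.96 points.
- Detectable difference = (1.960 + 0.842) × 1.96 = 5.5 points.

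An ICC of about 0.032 at a 20% control rate, or 0.016 at 40%, gives the same 5.5. The stated figure is therefore plausible with no site component at all.

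**2. Implied standard error.** 5.5/(1.960 + 0.842) = 1.963 points.

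**3. Add residual site variation.** With SD_site the between-site SD left after adjustment and sites of equal weight:

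Total SE = √[1.963² + (1/3 + 1/2) × SD_site²]

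For example, at SD 2: √(3.854 + 3.333) = 2.68.
- Type I error of the clinician-level test = 2Φ(−1.96 × 1.963/total SE).
- Normal-reference power for 5.5 points uses a two-sided 5% z test with the total SE.
- Site-level power uses a noncentral t with 5 − 2 = 3 df, critical value 3.182 and noncentrality 5.5/total SE.

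| Residual site SD (points, assumed) | Total SE | Type I error, clinician-level test | Power, z with total SE | Power, site as unit (3 df) |
|---|---|---|---|---|
| 0 | 1.96 | 5.0% | 80% | 48% |
| 1 | 2.17 | 7.6% | 72% | 42% |
| 2 | 2.68 | 15.1% | 54% | 30% |
| 3 | 3.37 | 25.3% | 37% | 21% |

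Type I error reaches 10% at a residual site SD of about 1.4 points.

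**4. Does the exploratory clinic-level clustering cure this?** Section 7.2.3 does not say what a clinic is. It could be the five education sites (6.7), the eight named locations (6.2) or the 35 outpatient clinics (6.3). Only the first is the unit of assignment, and five clusters are too few for a standard sandwich estimator. In simulation under the null, with five equal sites split 3 and 2, even the simple finite-cluster scaling with a t(4) reference rejected about 11% of the time. An exact permutation of 3 against 2 sites has 10 allocations, so its smallest possible p-value is 0.10.

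**The case against.** **The plan already treats education as observational.** It declares the assignment non-random, adjusts for baseline prescribing, drops clinicians who were not present throughout, and limits the primary education analysis to the period before delayed education. Education is secondary in Section 6.1 and absent from the hypotheses in Section 5.2. All of this stands and limits the weight of the point. Adjustment may shrink site differences, but it does not make five assigned units into more.

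**The error rates depend on an assumed site SD.** This also stands. If the residual site SD is zero, the clinician-level test is valid. Holding the standard error at 1.96 slightly overstates the inflation, because the clustered standard error absorbs a little site variance; in simulation, the 25% at SD 3 becomes about 24%. A reader might infer that the true error rate is 15% or 25%; no figure in the documents supports that.

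**The 48% is a cost of the site-level test, not an error in Section 7.1.** Agreed. A reader might infer that the 5.5-point figure is miscalculated or that 48% is a ceiling. Neither follows. Step 1 shows that the figure is plausible at its own level, Section 7.1 does not say whether site effects were simulated, and baseline adjustment could reduce the standard error. Nor would a 3-df test remove confounding; with non-random assignment, part of any site difference is bias.

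**A reader might infer that the CDS results are compromised too.** Section 7.2.2 applies to the education terms in the CDS models the rule "We will retain both terms if the interaction is significant and retain the main effect if only it is significant". The documents do not support that inference. CDS was randomized by clinician, with non-HF specialists stratified by location, so a shared site effect largely cancels from CDS contrasts. In a simulation with CDS balanced within site (assumed), the CDS-by-education interaction test rejected 5.0, 4.8 and 4.5% at site SD 0, 2 and 3, against 4.8, 15 and 24% for the education main effect. Only site variation in the CDS effect itself would inflate the interaction test, and the documents give nothing on that.

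**Conclusion.** The concern holds for the education comparison only. Its standard errors and power claim sit below the unit of assignment, and the planned p<0.05 rule would turn a non-random contrast of five sites into a significance verdict. If any site difference remains after adjustment, over-rejection follows, and the stated 80% can be taken at face value only if there is none. The size is conditional on a residual site SD that the documents do not give: type I error of about 5 to 25% and site-level power of about 48 to 21% over 0 to 3 points, at an unchanged clinician-level standard error. The Abstract's description of education as randomized contradicts Section 7.2.2, whatever the size. This should be fixed, with limited weight, because the trial's hypotheses concern CDS and those contrasts are not materially affected.

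**What to change.** 1. **Abstract, Interventions bullet:** remove the word randomized for education timing, to agree with Section 7.2.2.
2. **Sections 7.2.2 and 7.2.3:** label the education comparison non-randomized and exploratory. Show the five site-level results beside the baseline-adjusted estimate. Draw no p<0.05 conclusion about education from clinician-clustered standard errors alone. Say which unit clinic means.
3. **Section 7.1:** state that the 80%/5.5-point education figure assumes no residual site variation. Alternatively, restate it with site as the unit, giving the assumed control rate, clinician and site ICCs, and the N after the limits in Sections 7.2.2 and 10.

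**Cost.** Wording in four places and one five-row table, with no new data. The education comparison loses its significance claim and its stated power. Item 3 is reporting only: both education waves have started, so it cannot change the design. Section 10 says outcomes had not been extracted or examined by arm, apart from a very limited check of the alerts, so on that account the changes can be made before results are seen.
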